8.2.3. Final Analysis

The final analysis will be conducted after the collection of the last data point for the last patient (i.e. study end). The final analysis will be an addendum of the preliminary final analysis for any data collected since the time of the previous analysis.

8.2.4. Missing, Unused and Spurious Data

Safety run-in

There will be no data imputation for missing data in the primary endpoint (DLTs). Procedures for accounting for missing, unused and spurious PK concentration-time data will be determined by the PK parameter derivation rules of the PK scientist. The PK parameter derivation rules will not be documented in the SAP.

Phase IIa

For the primary analysis, there will be no data imputation for missing data in the primary endpoint.

Imputation methods may be proposed for purposes of sensitivity analysis. Imputation methods for missing data in the primary endpoint and secondary endpoints will be fully documented in the SAP, if any.

8.2.5. Deviations from the Statistical Plan

Any deviation(s) from the final statistical plan in the final analysis will be described and justification given in the final report.

8.2.6. Efficacy Analysis

All patients will be included in the efficacy analysis.

To be considered ‘evaluable’ for the primary efficacy analysis, a patient must have a week 12 (± 1 week) tumour measurement or evidence of progression prior to week 12.

8.2.7. Primary Analysis

The primary endpoint of change in tumour size at week 12 (or progression if prior to week 12) will be assessed in all patients. The data cut-off for the primary endpoint will occur 12 weeks after the last subject has entered the study.

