5. STUDY PLAN AND PROCEDURES

5.1. Study Schedules

Scheduled visits are uniquely identified by study period, and day within the period. The combination treatment period of the safety run-in study and the phase IIa study are further partitioned into consecutively numbered treatment cycles of 28 days duration. The period and day when scheduled visits occur, as well as, observations and assessments required during the study are summarised in Table 1 for the safety run-in and Table 2 for phase IIa.

In the phase IIa study, unless indicated otherwise, scheduled assessments may take place within ± 1 day of the scheduled day, e.g, laboratory evaluations scheduled for cycle 1 day 7 may take place on cycle 1 day 6 or day 8. Assessment days will all be relative to the start of study treatment, i.e. Cycle 1 Day 1.

If a patient has AZD4547 treatment breaks, please contact the Study Team for advice regarding appropriate timing of PD biomarker assessments. All other assessments, including laboratory safety assessments, vital signs and RECIST should continue to be performed as described in the appropriate sections of the protocol, relative to the baseline assessments

Table 1: Study Plan (Safety run-in)

Study Period	Screening	NSAI ¹ monotherapy		AZD4547 + NSAI ¹ combination								AZD4547 / NSAI ¹ Discont.	28-day follow-up
		n/a		Cycle 1				Cycle 2		Cycle 3	Cycle 4 (onwards)		
Activity / Day	-28 to -1	1	7	1	7	15	21	1	15	1	1		
Inclusion/exclusion criteria & informed consent	X												
Demographics	X												
Medical history / Concomitant medical conditions	X	X	X	X	X	X	X	X		X	X	X	
Radiotherapy (previous/current) ²	X	X	X	X	X	X	X	X		X	X	X	X
Chemotherapy (previous/current)	X												X
Surgical History	X												
Disease Extent/Tumour Characteristics	X												
Concomitant medication	X	X	X	X	X	X	X	X		X	X	X	X
Prohibited medication	X												
Physical examination	X	X	X					X		X	X	X	
ECOG performance status	X	X	X		X	X	X	X		X	X	X	X
Vital signs	X		X					X		X	X	X	X
ECG	X				X			X		X	X	X	
Echo / MUGA scan	X							X ³				X	
Laboratory evaluations (blood/urine)	X		X		X	X	X	X		X	X	X	X

Study Period	Screening	NSAI ¹ monotherapy		AZD4547 + NSAI ¹ combination								AZD4547 / NSAI ¹ Discont.	28-day follow-up
		Cycle	n/a	Cycle 1				Cycle 2	Cycle 3	Cycle 4 (onwards)			
Activity / Day	-28 to -1	1	7	1	7	15	21	1	15	1	1		
Ophthalmic assessment	X							X		X	X ⁴	X	
Treatment compliance			X	X	X	X	X	X		X	X	X	
PI disease status assessments	X								X		X		

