5.2.21. Tumour Assessments (Phase IIa only)

Tumour assessments will be performed using CT or MRI scans of the chest, abdomen and pelvis. The same method used for assessment at baseline must be used at all subsequent time points.

Tumour assessment will include: if disease is measurable or non-measurable (at least one lesion must be measurable), date of assessment, imaging method used, site (breast, lung, liver, pleural effusion, local lymph nodes, distant lymph nodes, bone, brain or other site), longest diameter of each target lesion and sum of longest diameters for all target lesions.

Patient response to treatment will be assessed using RECIST v1.1 criteria. Tumour size, Progression Free Survival and Objective Response Rate will all be determined.

Tumour Size, will be assessed at baseline and on scans at subsequent time points and recorded as the sum of the longest diameters of the target lesions.

Progression Free Survival (PFS) is defined by the progression criteria of RECIST.

Objective Response Rate (ORR) is defined as the percentage of patients who have at least one visit response of CR or PR prior to any evidence of progression (as defined by RECIST v1.1)

The RECIST v1.1 (January 2009) guidelines for measurable, non-measurable, target and non-target lesions and the objective tumour response criteria (complete response, partial response, stable disease or progression of disease) are detailed in Appendix A

Baseline assessment should be performed no more than 28 days before the start of study treatment and ideally as close as possible to the start of study treatment; it should include all areas known for possible breast cancer metastases.

Subsequent tumour assessments will be conducted at week 6, week 12 (primary endpoint) and then every 8 weeks until objective disease progression or cessation of study treatment and finally at AZD4547 discontinuation visit. The window for each assessment is ± 1 week.

Duplicates will be made of all CT/MRI scans. These duplicate scans will be collected to enable an independent review of progression.

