8.2.2. Preliminary Final Analysis

Since the study has follow up of efficacy and safety endpoints beyond 12 weeks, the preliminary final analysis may be conducted as soon as the database can be soft locked for the primary endpoint data accumulated up to 12 weeks after the last subject enters the study.

The analysis of primary endpoint, i.e. change in tumour size at 12 weeks (or progression if prior to week 12), will be performed on completed cases only. To assess the effect of early drop out (due to death or withdrawal before 12 week follow up scan or progression, for example) change in tumour size at 6 weeks will also be calculated and the results compared to the primary analysis. Subjects with only baseline measures will be excluded from the analysis.

The study data will be summarised using standard descriptive methods. Histograms and box-plots will be used to assess the distributional assumptions and to check for possible outliers. Mathematical transformations will be applied, where appropriate, in order to render variables normally distributed. Continuous variables that follow an approximately normal distribution will be summarised using the mean and standard deviation. Skewed continuous variables will be summarised using the median and inter-quartile range. Categorical variables (binary, ordered and multinomial) will be presented in terms of frequencies and percentages. Where possible, the relationship between the outcomes and other variables will be explored graphically, using scatter plots and box-plots prior to model fitting. Change in tumour size at 12 weeks for each patient will

be shown graphically in a “waterfall plot” with subgroups based on tumour response and objective response highlighted in different colours to identify possible patterns.

The comprehensive statistical analysis plan (SAP) will be finalised prior to preliminary final analysis.

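### The primary-endpoint cut-off, 12 weeks after last entry, falls at least a week before the week 12 (± 1 week) scan window closes for the last patients

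*Protocol*

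**What the plan says.** Protocol 8.2.7 has the primary endpoint assessed in all patients and then fixes the date: "The data cut-off for the primary endpoint will occur 12 weeks after the last subject has entered the study". Section 8.2.2 allows the preliminary final analysis once the database can be "soft locked for the primary endpoint data accumulated up to 12 weeks after the last subject enters the study".

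Three other sections govern which scans count:

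- 8.2.6, evaluability: "a patient must have a week 12 (± 1 week) tumour measurement or evidence of progression prior to week 12".
- 5.2.21, scan timing: "The window for each assessment is ± 1 week".
- 5.1, time origin: "Assessment days will all be relative to the start of study treatment, i.e. Cycle 1 Day 1".

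The primary analysis uses completed cases only (8.2.2) and does not impute the primary endpoint (8.2.4). Section 8.2.3 plans a final analysis after the last data point, as an addendum covering data collected since the preliminary one.

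**The concern.** Two rules written for the same endpoint do not fit together. One accepts a scan up to 13 weeks after treatment starts. The other stops the data 12 weeks after the last patient enters, with no allowance for the window. The clocks also start at different points, and treatment cannot start before entry, so any difference lengthens the shortfall.

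A patient whose scan complies with 5.2.21 but falls after the cut-off has no week 12 value in the preliminary final analysis, and nothing is imputed. The omission is also selective. A late-enrolled patient with progression at the week 6 scan is already evaluable under 8.2.6, whereas a patient still free of progression and scanned in the second half of the window is not.

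**Working it through.** **Inputs.** 50 phase IIa patients (3.1); recruitment over 24 months (8.2.8); SD 0.30 for change in log tumour size and a two-sided 95% interval (8.1); window ± 1 week (5.2.21, 8.2.6). Assumptions: uniform accrual, and a lag L from study entry to Cycle 1 Day 1 of 0 to 4 weeks. The protocol states no lag. Four weeks is used as the upper end because screening spans the 28 days before treatment.

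**1. The plan's own precision.** 1.96 × 0.30/√50 = 0.083, and exp(0.083) = 1.09. Both figures in 8.1 are reproduced.

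**2. Timing.** Measured from the last patient's entry, the cut-off is at week 12 and the window runs from L + 11 to L + 13 weeks. The shortfall is (L + 13) − 12 = L + 1 weeks. It is 1 week with no lag and 5 weeks with a lag of 4.

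**3. Patients exposed.** Accrual is 50/(24 × 365.25/12/7) = 50/104.4 = 0.479 per week. Patients whose window is still open at the cut-off number about 1 + 0.479 × (L + 1): the last patient plus those who entered in the preceding L + 1 weeks.

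Not all of them would be scanned late. Suppose scan dates spread evenly over the two-week window (a further assumption). With L = 0 the last patient has a chance of 1/2 of a scan after the cut-off, and patients who entered in the week before average 1/4, giving 0.5 + 0.479 × 0.25. With L of 1 or more, the expected number is 1 + 0.479 × L.

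| Lag L (weeks) | Window, weeks after entry | Window open at cut-off | Expected scans after cut-off |
|---|---|---|---|
| 0 | 11-13 | 1.5 | 0.6 |
| 1 | 12-14 | 2.0 | 1.5 |
| 2 | 13-15 | 2.4 | 2.0 |
| 4 | 15-17 | 3.4 | 2.9 |

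**4. Selection.** The week 6 scan is due no later than week 7 after Cycle 1 Day 1, which is week L + 7 after entry. With L up to 4 this is week 11 at the latest, before the cut-off. Progression found at that scan is therefore always in the data, whereas a permitted week 12-13 scan may not be.

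**5. Effect on precision.** If every exposed patient were omitted:

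| n analysed | Half-width, log scale | Factor |
|---|---|---|
| 50 | 0.083 | 1.09 |
| 49 | 0.084 | 1.09 |
| 48 | 0.085 | 1.09 |
| 47 | 0.086 | 1.09 |
| 46 | 0.087 | 1.09 |

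**6. Effect on the mean.** If k of 50 patients are omitted and their mean differs from that of the rest by d, the estimate shifts by (k/50) × d. Taking d as one full SD, 0.30 (an illustrative assumption), the shift is 0.012 for k = 2 and 0.024 for k = 4. Both are small against a half-width of 0.083.

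**The case against.** The strongest reply is that nothing disappears. A reader might infer that the late scans are lost to the trial, and the protocol does not support that: 8.2.3 provides a final analysis after the last data point and an addendum for later data. This stands as mitigation. It does not settle the matter, because 8.2.7 sets a cut-off specific to the primary endpoint and 8.2.3 does not say that the primary estimate is recalculated.

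A reader might also infer that the cut-off precedes the whole scan window, or that a scan on the nominal day is missed. Neither follows from the text alone. With no lag the cut-off falls in the middle of the window, and scans in weeks 11 to 12, the nominal day included, are kept. The nominal day is missed only if entry precedes Cycle 1 Day 1. Section 7.2 links a study entry form to confirmation of eligibility, and 5.5.1.3 with note 9 of Table 2 places the optional first biopsy between that confirmation and treatment, so a gap is plausible for some patients. Yet no section defines study entry for 8.2.7 or gives the length of the gap.

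The numbers are small, too. With no lag the expected count is below one patient. Some of the exposed will have progressed early and so be evaluable anyway: with the 6-month median in 8.2.8 and exponential times (assumed), 1 − 0.5^(1.38/6) = 15% by week 6. A sensible team might also simply wait, since 8.2.2 only permits the early analysis. That last argument is the weakest: 8.2.7 states the cut-off as a fixed date, and in an open-label single-arm study the choice should not be left to the time of analysis.

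**Conclusion.** The point holds as a contradiction between the cut-off in 8.2.7 and 8.2.2 and the evaluability window in 5.2.21 and 8.2.6. The one-week shortfall follows from the text alone. Anything beyond one week rests on an assumed lag between entry and treatment.

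The consequence is limited to possible omission from the primary (preliminary final) analysis of about one or two of 50 patients, or about three with a lag of several weeks. These counts assume uniform accrual and are upper figures for each lag; faster recruitment at the end would raise them. The case rests on the inconsistency and on the selective omission of patients without early progression. It does not rest on precision, which barely changes. It is worth correcting because the correction is specific and nearly free.

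**What to change.** In 8.2.7, replace the cut-off with 13 weeks after the last patient's Cycle 1 Day 1, meaning the latest such date in the study. Use the same definition for the soft lock in 8.2.2. The cut-off then covers the full window in 8.2.6 and uses the same time origin as 5.1, so the undefined term study entry no longer matters here.

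No extra allowance for scan reporting is needed in the cut-off, because the soft lock in 8.2.2 already waits for the data to be ready.

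The cost is two amended sentences and a later preliminary analysis: one week plus any lag from entry to treatment, hence one to five weeks over the assumed range. Sample size and planned precision do not change.

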8.2.8. Secondary Analyses

Frequency tabulations of the tumour response RECIST criteria and 2-category ORR will be presented.

As median time to progression is expected to be 6 months and the recruitment period to be 24 months, the analysis of PFS will take place at 30 months (when each subject has been followed up to progression or for a minimum of 6 months). At this time we anticipate that 95% of subjects will have progressed on study treatment.

8.2.9. Safety Analysis

All patients who receive at least one dose of study treatment will be included in the safety analysis set. Safety data will not be formally analysed. Safety and tolerability data will be presented by treatment received.

9. REGULATORY, ETHICAL AND LEGAL ISSUES

9.1. Declaration of Helsinki

The investigator will ensure that this study is conducted in full conformity with the principles of the 1964 Declaration of Helsinki and any subsequent revisions.

9.2. Good Clinical Practice

The study will be conducted in accordance with the guidelines laid down by the International Conference on Harmonisation for Good Clinical Practice (ICH GCP E6 guidelines).

9.3. Independent Ethics Committee/Institutional Review Board Approval

9.3.1. Initial Approval

Prior to the shipment of IMP and the enrolment of subjects, the IEC/IRB must provide written approval of: the conduct of the study at named sites, the protocol and any amendments, the Subject Information Sheet and Consent Form, any other written information that will be provided to the subjects, any advertisements that will be used and details of any subject compensation.

9.3.2. Approval of Amendments

Proposed amendments to the protocol and aforementioned documents must be submitted to the IEC/IRB for approval. Amendments requiring IEC/IRB approval may be implemented only after a copy of the IEC/IRB's approval letter has been obtained.

Amendments that are intended to eliminate an apparent immediate hazard to subjects may be implemented prior to receiving Sponsor or IEC/IRB approval. However, in this case, approval must be obtained as soon as possible after implementation.

9.3.3. Annual Safety Reports and End of Trial Notification

The IEC/IRB will be sent annual safety updates in order to facilitate their continuing review of the study (reference. ICH GCP E6 Section 3.1.4) and will also be informed about the end of the trial, within the required timelines.

9.4. Regulatory Authority Approval

The study will be performed in compliance with the regulatory requirements of the United Kingdom. Clinical Trial Authorisation from the appropriate Regulatory Authority must be sought/obtained prior to the start of the study. In addition, the Regulatory Authority must approve amendments (as instructed by the Sponsor), receive SUSAR reports and annual safety updates, and be notified of the end of the trial.

9.5. Insurance

The Sponsor has civil liability insurance, which covers this study in the United Kingdom.

9.6. Informed Consent

The Principal Investigator at each site will:

- Ensure that each patient is given full and adequate oral and written information about the study including the background, purpose and risks/benefits of participation
- Ensure that each patient is notified that they are free to withdraw from the study at any time

- Ensure that each patient is given the opportunity to ask questions and allowed sufficient time to read and understand the information sheet
- Ensure each patient provides signed, dated informed consent before undergoing any study specific procedure
- Ensure the original copy of the signed, dated Informed Consent Form is stored in the patient's medical records and a copy is also filed in the Investigator site file
- Ensure that each patient receives a copy of the signed, dated Informed Consent Form

9.7. Contact with General Practitioner

It is the investigator's responsibility to inform the subject's General Practitioner (where applicable) by letter that the subject is taking part in the study provided the subject agrees to this, and information to this effect is included in the Subject Information Sheet and Informed Consent. A copy of the letter should be filed in the Investigator Site File.

9.8. Subject Confidentiality

The investigator must ensure that the subject's privacy is maintained. On the CRF or other documents submitted to the Sponsors, subjects will be identified by a trial ID number only. Documents that are not submitted to the Sponsor (e.g. signed informed consent form) should be kept in a strictly confidential file by the investigator.

The investigator shall permit direct access to subjects' records and source document for the purposes of monitoring, auditing, or inspection by the Sponsor, authorised representatives of the Sponsor, Regulatory Authorities and IECs / IRBs.

9.9. Data Protection

Precautions will be taken to ensure that patient confidentiality is preserved at all times. The Patient Consent form will identify those individuals who will require access to patient data and identifiable details and obtain appropriate permission from the consenting patient.

9.10. End of Trial

The end of the trial is defined as collection of the last data point for the last patient.

9.11. Study Documentation and Data Storage

The investigator must retain essential documents until notified by the Sponsor (Imperial College London), and at least for ten years after study completion, as per Imperial College London policy. Subject files and other source data (including copies of protocols, CRFs, original reports of test results, IMP dispensing logs, correspondence, records of informed consent, and other documents pertaining to the conduct of the study) must be kept for the maximum period of time permitted by the institution. Documents should be stored in such a way that they can be accessed/data retrieved at a later date. Consideration should be given to security and environmental risks.

No study document will be destroyed without prior written agreement between the Sponsor and the investigator. Should the investigator wish to assign the study records to another party or move them to another location, written agreement must be obtained from the Sponsor.

10. DATA AND STUDY MANAGEMENT

10.1. Source Data

All original records and certified copies of original records of clinical findings, observations, or other activities necessary for the reconstruction and evaluation of the trial are classified as source data. Source data are contained in source documents; these are defined as: original documents, data, and records e.g., hospital records, clinical and office charts, laboratory notes, memoranda, subjects' diaries or evaluation checklists, pharmacy dispensing records, recorded data from automated instruments, copies or transcriptions certified after verification as being accurate copies, microfiches, photographic negatives, microfilm or magnetic media, x-rays, subject files, and records kept at the pharmacy, at the laboratories and at medico-technical departments involved in the clinical trial.

10.2. Language

CRFs will be in English. Generic names for concomitant medications should be recorded in the CRF wherever possible. All written material to be used by subjects must use vocabulary that is clearly understood, and be in the language appropriate for the study site.

10.3. Data Collection

In compliance with Good Clinical Practice (GCP), the medical records/medical notes should be clearly marked and allow easy identification of a patient's participation in the clinical trial

The Investigator (or delegated member of the site study team) must record all data relating to protocol procedures, IMP administration, laboratory data, safety data and efficacy data into the trial InForm electronic data collection (EDC) system.

10.4. Electronic Recording of data

Full details for procedures for completion of eCRFs will be provided in the study manual.

10.5. Data Management

Data management will be performed by the Imperial Clinical Trials Unit – Section on Cancer using the InForm electronic data capture (EDC) and management system. The system allows for real time oversight of trial activity including adverse event reporting, rapid data validation and data aggregation.

AE data will be coded using the Medical Dictionary for Regulatory Activities (MedDRA) system organ class and preferred term, and CTCAE grade.

Data queries will be raised for inconsistent, impossible or missing data. All entries to the study database will be available in an audit trail.

